5.1.1.2. Clinical Pharmacology Summary

Nivolumab PK was assessed using a PPK approach for both single-agent nivolumab and nivolumab with ipilimumab.

Nivolumab as a single agent: The PK of single-agent nivolumab was studied in patients over a dose range of 0.1 to 20 mg/kg administered as a single dose or as multiple doses of nivolumab as a 60-minute intravenous infusion every 2 or 3 weeks. Nivolumab clearance

decreases over time, with a mean maximal reduction (% coefficient of variation [CV%]) from baseline values of 24.5% (47.6%) resulting in a geometric mean steady-state clearance (CL_{ss}) (CV%) of 8.2 mL/h (53.9%) in patients with metastatic tumors; the decrease in CL_{ss} is not considered clinically relevant. Nivolumab clearance does not decrease over time in patients with completely resected melanoma, as the geometric mean population clearance is 24% lower in this patient population compared with patients with metastatic melanoma at steady state. The geometric mean volume of distribution at steady state (CV%) is 6.8 L (27.3%), and geometric mean elimination half-life is 25 days (77.5%). Steady-state concentrations of nivolumab were reached by 12 weeks when administered at 3 mg/kg every 2 weeks, and systemic accumulation was 3.7-fold. The exposure to nivolumab increases dose proportionally over the dose range of 0.1 to 10 mg/kg administered every 2 weeks. The predicted exposure (C_{avg} and C_{max}) of nivolumab after a 30-minute infusion is comparable to that observed with a 60-minute infusion.

Specific Populations: The PPK analysis suggested that the following factors had no clinically important effect on the clearance of nivolumab: age (29 to 87 years), weight (35 to 160 kg), gender, race, baseline lactate dehydrogenase, PD-L1 expression, solid tumor type, tumor size, renal impairment, and mild hepatic impairment.

Renal Impairment: The effect of renal impairment on the clearance of nivolumab was evaluated by a PPK analysis in patients with mild (eGFR 60 to 89 mL/min/1.73 m²), moderate (eGFR 30 to 59 mL/min/1.73 m²), or severe (eGFR 15 to 29 mL/min/1.73 m²) renal impairment. No clinically important differences in the clearance of nivolumab were found between patients with renal impairment and patients with normal renal function.

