7.6.1. Adverse Events

AEs should be monitored from the time that the informed consent is signed through 100 days after the last dose of study treatment (both CMP-001 and nivolumab) or until an alternative cancer treatment is initiated, whichever occurs first, for all subjects. All AEs from the time that the informed consent is signed will be captured on the eCRF. Subjects who discontinue CMP-001 but remain on treatment with nivolumab will continue to have AEs collected according to this schedule until 100 days after the last dose of nivolumab or until an alternative cancer treatment is initiated, whichever occurs first.

Treatment-related SAEs starting more than 100 days after the last dose of study treatment will be recorded on the AE eCRF.

Immune-mediated AEs are AEs consistent with an immune-mediated mechanism or immunemediated component for which non-inflammatory etiologies (eg, infection or tumor progression) have been ruled out. Immune-mediated AEs can include events with an alternate etiology that were exacerbated by the induction of autoimmunity. Information supporting the assessment will be collected on the participant's case report form.

See Section 8.3 for a full description of the collection and reporting of AEs during this study.

7.7. 100-Day Follow-up Contact

The 100-Day Follow-up contact is a safety follow-up visit that should be conducted in the study clinic or via phone. The subject should be questioned for any new AEs, resolution of prior AEs, and use of concomitant medications, including other cancer treatments. No other safety assessments are required unless the Investigator identifies a new safety concern that requires further follow-up.

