8.3.1. Reporting Serious Adverse Events

All SAEs and associated source documents must be reported in written or typed English via completion of the eCRF AE page and accompanying paper SAE Report Form to IQVIA Biotech Safety (following the same reporting process outlined in Section 8.3.) within 24 hours of first knowledge of the event regardless of relationship to the study procedures or individual study treatments. The paper SAE Report form should be used to record pertinent information regarding the SAE. The Investigator is requested to supply as much detailed information as possible regarding the event at the time of the initial report.

Serious adverse events will be collected from the time of ICF until 100 days after the last dose of study treatment or until an alternative cancer treatment is initiated, whichever occurs first. Any SAE considered to have at least possible relationship to the study treatment and discovered by the Investigator at any time period after EOT should be reported throughout the study period.

If at any time after the subject has completed participation in the study, the Investigator or study staff becomes aware of an SAE during the study reporting period that they believe is possibly, probably, or definitely related to either study treatment (see Section 8.2.2.), then the event and any known details must be reported promptly to the Sponsor or its representatives. The following reporting instructions must be followed.

At minimum, the Investigator will be asked to provide the following information:

- For the initial SAE notification, the Investigator must provide, at a minimum, basic information such as the protocol number, subject's year of birth or age at onset, subject ID number, period of study treatment intake, event term, nature of the event, detailed description of the event, seriousness criteria, causality of the event to CMP-001 and to nivolumab separately, and severity
- In addition, the initial SAE information entered on the eCRF and paper SAE Report Form should include all pertinent known information about the SAE and the affected subject, such as the following: subject sex; description of the AE including reason for assessment as serious; and individual study treatment information including doses, dates of dosing, and action taken with individual study treatments

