APPENDIX J. WOMEN OF CHILDBEARING POTENTIAL DEFINITION AND METHODS OF CONTRACEPTION

DEFINITIONS

Woman of Childbearing Potential (WOCBP)

A woman is considered fertile following menarche and until becoming post-menopausal unless permanently sterile. Permanent sterilization methods include hysterectomy, bilateral salpingectomy, and bilateral oophorectomy.

Women in the following categories are not considered WOCBP

- Premenarchal
- Premenopausal female with 1 of the following:
- Documented hysterectomy
- Documented bilateral salpingectomy
- Documented bilateral oophorectomy

Note: Documentation can come from the site personnel's review of the participant's medical records, medical examination, or medical history interview.

- Postmenopausal female
 - A postmenopausal state is defined as 12 months of amenorthea in a woman over age 45 years in the absence of other biological or physiological causes. In addition, females under the age of 55 years must have a serum follicle stimulating hormone, (FSH) level > 40 mIU/mL to confirm menopause.

CONTRACEPTION GUIDANCE FOR FEMALE PARTICIPANTS OF CHILD BEARING POTENTIAL

One of the highly effective methods of contraception listed below is required during study duration and until the end of relevant systemic exposure, defined as 5 months after the end of study treatment.*

Highly Effective Contraceptiv	e Methods That	Are User Dependent
Inginy Enecuve Contraceput	e methous rha	Ale User Dependent

Failure rate of <1% per year when used consistently and correctly.^a

 Combined (estrogen- and progestogen-containing) hormonal contraception associated with inhibition of ovulation^b

- oral

- intravaginal
- transdermal
- Progestogen-only hormonal contraception associated with inhibition of ovulation^b
 - oral
 - injectable

Highly Effective Methods That Are User Independent

- Implantable progestogen-only hormonal contraception associated with inhibition of ovulation ^b
- Intrauterine hormone-releasing system (IUS)^c
- Intrauterine device (IUD)^c
- Bilateral tubal occlusion
- Vasectomized partner

A vasectomized partner is a highly effective contraception method provided that the partner is the sole male sexual partner of the WOCBP and the absence of sperm has been confirmed. If not, an additional highly effective method of contraception should be used.

Sexual abstinence

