### Statistical Analysis Plan

Regeneron Pharmaceuticals Inc. / Protocol: CMP-001-010 IQVIA Biotech (Confidential) Project # RZA44091

• The Investigator and Medical Monitor agree that follow-up is no longer necessary

Adverse event (AE) data are available to the Sponsor from two sources: the eCRFs and the Serious Adverse Event (SAE) paper forms and corresponding SAE narratives. While reconciliation will be performed to ensure consistency between the two types of data, the production of data summaries and listings will be based on the data collected on the eCRF.

*Treatment-emergent adverse event (TEAE)* 

Pretreatment AEs are AEs that occur from the time of informed consent up to the first dose of study treatment (W1D1). A treatment-emergent adverse event (TEAE) is defined as an AE that started or worsened in severity on or after the date that study treatment was first administered (W1D1) until 100 days after the last dose of study treatment or a new cancer treatment is initiated, whichever occurs first.

Treatment-emergent adverse events will be coded using MedDRA (version 23.1 or later) and data will be summarized for the Safety Analysis Set. The number and percent of subjects reporting each TEAE will be summarized, as well as the number of TEAEs. A subject with 2 or more TEAEs within the same level of summarization (i.e., system organ class or preferred term) will be counted only once in that level using the most severe event or most related (for the relationship to study treatment tables).

AEs are graded using Common Terminology Criteria for Adverse Events (CTCAE) Version 5.0. AE summaries may include summaries for all AEs and by the maximum CTCAE grade for the item being summarized (i.e., SOC or PT). In these cases, the outputs will include a row for All Grades as well as rows for the 5 potential CTCAE grades: Grade 1 (Mild), Grade 2 (Moderate), Grade 3 (Severe), Grade 4 (Life threatening or disabling), or Grade 5 (Death).

If grade is missing for a TEAE, the event will be counted as grade 3=severe in the TEAE summary tables. If relationship is missing for a TEAE, the event will be counted as related in the TEAE summary tables.

An AE preferred term reported by a subject more than once will be represented in the most severe category or most related (for the relationship to study treatment tables).

A TEAE summary table will be generated including the following (N (%)):

- Subjects with one or more TEAEs
- Subjects with TEAEs of grade 3 or higher

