## Statistical Analysis Plan

Regeneron Pharmaceuticals Inc. / Protocol: CMP-001-010 IQVIA Biotech (Confidential) Project # RZA44091

- Subjects with CMP-001 treatment-related TEAEs (includes TEAEs which are definitely, probably and possibly related and those with missing relationship)
- Subjects with Nivolumab treatment-related TEAEs (includes TEAEs which are definitely, probably and possibly related and those with missing relationship)
- Subjects with grade 3 or higher CMP-001 treatment-related TEAEs (includes TEAEs which are definitely, probably and possibly related and those with missing relationship)
- Subjects with grade 3 and higher Nivolumab treatment-related TEAEs (includes TEAEs which are definitely, probably and possibly related and those with missing relationship)
- Subjects with Serious AEs (SAEs)
- Subjects with CMP-001 treatment-related SAEs (includes TEAEs which are definitely, probably and possibly related and those with missing relationship)
- Subjects with Nivolumab treatment-related SAEs (includes TEAEs which are definitely, probably and possibly related and those with missing relationship)
- Subjects with TEAEs leading to CMP-001 treatment discontinuation
- Subjects with TEAEs leading to Nivolumab treatment discontinuation
- Subjects with immune-mediated AEs as assessed by the Investigator
- Subjects with TEAEs resulting in death

The following additional AE summaries by SOC/PT will be produced:

- All TEAEs
- Grade 3 or higher TEAEs
- TEAEs by maximum grade and maximum relationship
  - TEAEs related to any study drug (includes TEAEs which are definitely, probably and possibly related and those with missing relationship)
  - TEAEs related to CMP-001 (includes TEAEs which are definitely, probably and possibly related and those with missing relationship)
  - TEAEs related to Nivolumab (includes TEAEs which are definitely, probably and possibly related and those with missing relationship)
- TEAEs by maximum grade
- TEAEs by maximum relationship to CMP-001
- TEAEs by maximum relationship to Nivolumab

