### Statistical Analysis Plan

Regeneron Pharmaceuticals Inc. / Protocol: CMP-001-010 IQVIA Biotech (Confidential) Project # RZA44091

- Grade 3 or higher TEAEs related to CMP-001 (includes TEAEs which are definitely, probably and possibly related and those with missing relationship)
- Grade 3 or higher TEAEs related to Nivolumab (includes TEAEs which are definitely, probably and possibly related and those with missing relationship)
- TEAEs of Special Interest
- TEAEs resulting in death
- All SAEs
  - SAEs related to any study drug (includes TEAEs which are definitely, probably and possibly related and those with missing relationship)
  - SAEs related to CMP-001 (includes TEAEs which are definitely, probably and possibly related and those with missing relationship)
  - o SAEs related to Nivolumab (includes TEAEs which are definitely, probably and possibly related and those with missing relationship)
- TEAEs leading to treatment discontinuation of any study drug
- TEAEs leading to CMP-001 treatment discontinuation
- TEAEs leading to Nivolumab treatment discontinuation

A hierarchical listing will display the MedDRA system organ classes represented in the data. Within each system organ class, the listing will display each unique preferred term. Within each preferred term, the listing will display each unique verbatim (recorded) term. Listed terms will be ordered alphabetically.

The following AE listings will be produced:

- All TEAEs
- Grade 3 or higher TEAEs
- TEAEs considered related to study treatment (includes TEAEs which are definitely, probably and possibly related and those with missing relationship)
- TEAEs resulting in death
- SAEs
- Related SAEs. This listing will include serious TEAEs with a drug relationship of "Possibly Related," "Probably Related", "Definitely Related." It will also include serious TEAEs with missing drug relationships.
- TEAEs leading to treatment discontinuation

Regeneron Pharmaceuticals Inc. / Protocol: CMP-001-010 IQVIA Biotech (Confidential) Project # RZA44091

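### The SAP confines its Related SAEs listing, and on the natural reading its related-SAE counts, to TEAEs, leaving out late treatment-related SAEs that the protocol has sites record

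*SAP*

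**What the plan says.** **Collection.** Protocol 7.6.1 makes an explicit exception to the 100-day limit: "Treatment-related SAEs starting more than 100 days after the last dose of study treatment will be recorded on the AE eCRF". Section 8.3 repeats it, allowing events after day 100 onto the AE eCRF only if they are both serious and related. Section 8.3.1 adds a reporting duty for SAEs that are at least possibly related and "discovered by the Investigator at any time period after EOT should be reported throughout the study period". It also says that SAEs are reported through the eCRF AE page together with the paper form.

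**Analysis in the protocol.** Section 9.6.1 lists the planned AE summaries. Several carry the TEAE prefix, including those for Grade 3 or higher events, deaths and discontinuations. SAEs and related SAEs are named without it.

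**Analysis in the SAP.** Section IX.B defines a TEAE as an event starting or worsening from first dose "until 100 days after the last dose of study treatment or a new cancer treatment is initiated, whichever occurs first". It states that summaries and listings are built from the eCRF, and its own recording rule expects related events after day 100 to be there. For the Related SAEs listing it then says "This listing will include serious TEAEs with a drug relationship of" possible, probable or definite, and adds serious TEAEs with relationship missing. The overview row reads "Subjects with CMP-001 treatment-related SAEs (includes TEAEs which are definitely, probably and possibly related and those with missing relationship", and the SOC/PT table is described as "SAEs related to any study drug (includes TEAEs which are definitely, probably and possibly related and those with missing relationship"; the rows and tables for the individual drugs use the same gloss.

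**The concern.** The protocol goes out of its way to collect one kind of late event, the related SAE, and the SAP acknowledges that such events will be in the data. The SAP then defines the output named for those events so that the late ones cannot enter it. The omission is one-sided: it can lower the reported related-SAE results and can never raise them.

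There is also a risk of misreading. The related-SAE tables sit under All SAEs, which has no stated TEAE limit. If the total is unrestricted and the related sub-tables are TEAE-only, a late related SAE is in the first and not in the second. A reader who subtracts one from the other will count it as unrelated.

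**Working it through.** The plan gives no figure to reproduce here. The check is a reconciliation of definitions, followed by a small illustration of size.

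**Step 1: is the event in the data?** After day 100, yes: protocol 7.6.1 and 8.3 say so, and SAP IX.B agrees. The SAP sentence is in fact wider, since it drops the condition that the event be serious. Within 100 days but after new cancer therapy, routine collection has stopped under 7.6.1 and 8.3.1. Only the 8.3.1 duty for related SAEs found after end of treatment applies.

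**Step 2: is it a TEAE?** No in either case, under SAP IX.B and equally under protocol 8.1.3, which has the same window.

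**Step 3: trace three related SAEs through the SAP outputs** (days counted from last dose).

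| Event | Collected under | TEAE? | Related SAEs listing | Related-SAE rows and SOC/PT tables | SAEs listing, All SAEs table |
|---|---|---|---|---|---|
| Day 60, no new therapy | Routine collection | Yes | In | In | In |
| Day 110, no new therapy | Protocol 7.6.1, 8.3 | No | Out, explicitly | Out, on the natural reading | Can appear |
| Day 30, new therapy from day 25 | Protocol 8.3.1 only | No | Out, explicitly | Out, on the natural reading | Can appear, if reported |

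For the listing the restriction is stated outright. For the rows and tables it rests on the gloss, which says that TEAEs are included rather than that only TEAEs are. The natural reading is still exclusion: the rows belong to a table that the SAP calls a TEAE summary table, and no wording admits a non-TEAE to a related-SAE output.

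**Step 4: size per affected subject.** Input: 44 treated subjects (SAP II.C). One subject is 1/44 = 2.27%, or 2.3 percentage points. This applies only to a subject with no related SAE inside the window, because the rate counts subjects. If no other subject had a related SAE, the exact (Clopper-Pearson) 95% intervals would be:

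- 0/44 = 0% (0 to 8.0%)
- 1/44 = 2.3% (0.1 to 12.0%)
- 2/44 = 4.5% (0.6 to 15.5%)

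**Step 5: how likely is it to matter?** The documents give no rate of late related SAEs, so this is assumption only. For a per-subject probability p, the chance of at least one affected subject is 1 − (1 − p)^44. This gives 36% at p = 1%, 59% at 2%, 90% at 5% and 99% at 10%.

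**The case against.** The best defence has four parts.

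1. *The window is the protocol's own.* Protocol 8.1.3 has the same cut-off, and 9.6.1 itself limits deaths and Grade 3 or higher events to TEAEs. This stands. A reader might infer that the SAP wrongly truncates those outputs as well; the documents do not support that, because SAP and protocol agree on them. The mismatch is confined to related SAEs, which 9.6.1 names without the prefix. Section 9.6.1 asks for a related-SAE summary but not a related-SAE listing, so the listing is the SAP's addition; it should still show what its title says.

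2. *The gloss on the counts only explains which causality categories count as related.* That reading is possible. It leaves two programmers free to produce different counts, which is itself a reason to settle the wording.

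3. *The events are visible elsewhere.* This stands in part. It would be tempting to say that late related SAEs vanish from the report. They need not: the SAEs listing and the All SAEs table have no stated TEAE limit, and relationship to each drug is recorded for every AE, so a listing can show it. What is lost is their place in the results labelled related.

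4. *Late ascertainment is patchy.* Table 1 of the protocol schedules AE monitoring at posttreatment follow-up visits but not in long-term survival follow-up, and SAP II.F ends the study 100 days after the last subject's last dose. An open-ended count therefore mixes active and passive follow-up of unequal length. This stands, and it shapes the fix.

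A reader might also try to size the problem from drug persistence. The protocol puts contraception cover "until the end of relevant systemic exposure, defined as 5 months after the end of study treatment", and for nivolumab the "geometric mean elimination half-life is 25 days (77.5"% CV), which leaves 2^(−100/25) = 6.25% at day 100. Neither figure measures how often late related SAEs occur, and the 5-month period is contraception guidance rather than an AE window. The documents also do not name delayed immune toxicity as a specific risk or say how soon subjects start other therapy, so no bias can be estimated from those arguments.

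**Conclusion.** The inconsistency is real and worth correcting. Applied as written, the SAP excludes collected late related SAEs from the Related SAEs listing with certainty, and from the related-SAE rows and SOC/PT tables on the natural reading of the gloss. The related-SAE results can only be understated. The size is 2.3 percentage points for each of the 44 subjects whose only related SAE falls outside the window; the number of such subjects cannot be derived from the documents and may be zero.

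Confidence is highest for events after day 100, where the eCRF requirement is explicit. It is lower for events after new cancer therapy but within 100 days, which depend on 8.3.1 alone. The SAP's statement that it governs over the protocol (I.B) does not resolve the matter: the reason given there is the early stop of enrolment, and the SAP's own recording rule expects these events. The analyses are descriptive and exploratory, which limits the consequence, but safety is a secondary objective and the related-SAE count is one of the results a reader will carry away.

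**What to change.** In SAP IX.B, define the Related SAEs listing, the related-SAE rows of the overview table and the related-SAE SOC/PT tables as all SAEs with onset on or after first dose whose relationship is possible, probable, definite or missing, whether or not they fall inside the TEAE window. Flag events that start after day 100 or after new cancer therapy. Show the in-window count next to the full count, because ascertainment beyond the window is less complete.

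Related deaths outside the window are then captured through the related-SAE listing. The outputs for TEAEs resulting in death and for Grade 3 or higher TEAEs agree with the protocol and need not change.

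The cost is one sentence in the SAP and one flag variable in programming. No new data are needed. The reported related-SAE rate may come out slightly higher.
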